Urinary incontinence and cognitive impairment are common disorders in the elderly. Urinary incontinence has a profound negative impact on quality of life and is associated with depression, social isolation, physical inactivity, falls and fractures, caregiver burden, and institutionalization.¹⁻⁶ Urgency incontinence is one of the most prevalent types of urinary incontinence and, in community-dwelling women over the age of 60, the proportion of women with urgency incontinence doubles with each decade of advancing age.⁷⁻⁹ Similarly, cognitive impairment occurs in at least 10% of people over 65 years and in 50% of those over 85 years.¹⁰ Drug-related cognitive impairment is one of the few preventable etiologies of cognitive decline. Unfortunately, anti-cholinergic medications, including anti-cholinergic bladder medications, have been specifically implicated in the development of cognitive decline in older adults.¹¹⁻¹³ In 2012, the American Geriatrics Society updated the Beers Criteria for potentially inappropriate medications use in older adults to include a strong recommendation to avoid anticholinergic and antimuscarinic medications in this population.¹⁴ This poses a difficult dilemma for older adults who are at risk for both urgency incontinence and cognitive impairment, and lack treatment options for incontinence that do not cause or exacerbate cognitive impairment. Recently, the FDA approved a new category of medicine for urgency incontinence, a β -3 adrenergic receptor agonist (Mirabegron) that may have a better cognitive safety profile than anticholinergic drugs. However, in the absence of rigorous outcomes data confirming this, older adults and their clinicians may doubt the safety of and appropriateness of using Mirabegron to treat urgency incontinence in older age. Since incontinence and cognitive decline are common conditions that cause people to transition from living independently to assisted living facilities or nursing homes,¹⁵ it is imperative to identify therapies for urgency incontinence that don't contribute to cognitive decline; therapies that will improve quality of life by treating incontinence help elderly people to continue living independently.

Summary of the Proposed Pilot Trial

We propose a pilot study to assess the feasibility of enrolling ~50 community-dwelling, ambulatory women aged 65 years and older with urgency or mixed urgency predominate urinary incontinence into a randomized, controlled trial, to determine whether elderly women will adhere to an 8-week drug regimen and estimate the effect size necessary to show differences cognitive decline between Mirabegron and a standard anticholinergic therapy.

B. STUDY SYNOPSIS

Fifty community-dwelling women, ambulatory women with urgency or mixed urgency predominate urinary incontinence and at least 3 urgency incontinence episodes on a 3-day ~~screening diary, will be randomized to 8 weeks of Mirabegron (Myrbetriq) or tolterodine~~

tartrate (Detrol LA). The study will take place at the UCSF Women's Health Clinical Research Center.

C. SPECIFIC AIMS

The Specific Aims are to:

SA1: Assess the feasibility of enrolling and retaining women aged 65 years and older with urgency urinary incontinence in a randomized, controlled trial of an 8-week medication study.

SA2: To estimate preliminary differences in the effects of mirabegron compared to a standard anticholinergic therapy on cognitive function and calculate the standard deviation for: 1) a standard cognitive function battery, and 2) global patient perception of cognitive function.

SA3: To collect preliminary data on differences in change in physical function/mobility and other adverse events associated with Mirabegron vs. a standard anticholinergic therapy, such as dry mouth, constipation, vision, and falling.

SA4: Determine the differences in patient satisfaction between Mirabegron and a standard anticholinergic therapy in the treatment of urgency urinary incontinence.

SA5: To estimate preliminary differences in the efficacy of Mirabegron compared to a standard anticholinergic therapy on reducing urinary incontinence frequency, as assessed by validated 3-day voiding diary.

D. STUDY POPULATION

D1. Inclusion Criteria

Inclusion criteria reflect patients appropriate for treatment by primary care.

- Community-dwelling, ambulatory females \geq 65 years old

- Urgency or Mixed Urgency Predominate Urinary Incontinence (subject-reported) for ≥ 3 months prior to Screening (Visit 1)
- On a 3-day voiding diary, documentation of at least 3 urgency incontinence episodes with the number of urgency incontinence episodes greater than number of stress incontinence episodes
- Capability of understanding and having signed the informed consent form after full discussion of the research nature of the treatment and its risk and benefits
- Ability to perform all procedures and tests required by the protocol
- Report having a primary health care provider
- Willingness to remain on stable medication regime for duration of the randomized controlled trial. Participants will be asked to not add new medications during the randomized controlled trial, such as diuretics and other medications which may affect their voiding pattern unless deemed necessary by the participant's health care provider.

D2. Exclusion Criteria

Exclusion criteria reflect patients inappropriate for primary care and more appropriate for referral to a specialist.

- Seated blood pressure systolic >180 or diastolic >110 at Screening or Baseline
- Physician diagnosis of dementia
- Any use of dementia medications (donepezil (Aricept), galantamine (Razadyne), memantine (Namenda) , rivastigmine (Exelon)), or debilitating or recent neurologic disease
- Mini Mental State Examination (MMSE) score <20
- Geriatric Depression Scale (GDS) ≥ 6
- History of gastric retention, uncontrolled narrow angle glaucoma, myasthenia gravis, severe ulcerative colitis, toxic megacolon, fistula or a hole in your bladder or rectum, birth defect leading to urine leakage, and urine leakage starting in childhood
- Clinically significant hepatic dysfunction (Child-Pugh score B or greater) or renal insufficiency (creatinine clearance <30 mL/min or eGFR <30 mL/min/1.73 m²)
- Neurologic conditions such as stroke, multiple sclerosis, spinal cord injury, or Parkinson's disease.
- Major cardiovascular event in the past 6 months (i.e., MI, unstable angina, hospitalization for chest pain)
- Symptomatic pelvic organ prolapse defined as participant unable to completely empty her bladder within the past 3 months.
- History of surgery for incontinence, pelvic surgery (i.e., for prolapse or hysterectomy), intra-vesical therapy (e.g., botox), and/or bulk injections within the past 6 months.
- A known history of interstitial cystitis or a significant pain component associated with OAB symptoms, uninvestigated hematuria, urogenital cancer, radiation to the pelvis or external genitalia.
- Urinary tract infection (UTI) as shown by the results of the urinalysis at screening or recurrent urinary tract infection (RUTIs) defined as treatment for UTI >3 times in the last year.
- Urinary retention (post-void residual urine volume >150 cc measured by bladder scan at screening).

[figure not shown]
- Use of any electrostimulation, bladder training, or pelvic floor exercises (with certified incontinence practitioners) within 4 weeks of Screening.
- Use of mirabegron or tolterodine in the past 6 months.
- Has been treated within 4 weeks prior to Screening and/or is currently being treated with:
 - Any drug treatment for OAB
 - Any drugs with significant anticholinergic and antispasmodic effects (see exception for tricyclic antidepressants below)
- Has started treatment with or changed dose of tricyclic antidepressants or estrogens within 4 weeks prior to Screening.
- Intermittent use or unstable dose of diuretics. Treatment with diuretics initiated within 4 weeks prior to baseline and/or is not on a stable dose is not permitted.
- Treatment with potent CYP3A4 inhibitors, such as clarithromycin, ketoconazole, and itraconazole within 4 weeks prior to Screening.
- Administration of medications capable of inducing hepatic enzyme metabolism or transport (e.g., barbiturates, rifampicin, carbamazepine, phenytoin, primidone, or St. John's Wort) in the past 4 weeks.
- Administration of narrow therapeutic index drugs metabolized by CYP2D6, such as thioridazine, flecainide, and propafenone.
- Previously received any investigational drug within 30 days prior to trial entry.
- Alcohol and/or any other drug abuse in the opinion of the investigator.
- Participants who, in the opinion of the Investigator, have any medical (including known history of major hematological, renal, cardiovascular, or hepatic abnormalities) or psychological condition or social circumstances that would impair their ability to participate reliably in the trial, or those who may increase the risk to themselves or others by participating.
- Participants who, in the opinion of the investigator, are not likely to complete the trial for whatever reason.

Participants must meet all inclusion and exclusion criteria to be randomized to trial treatment.

E. STUDY DESIGN

Approximately 50 women with urgency or mixed urgency predominate urinary incontinence will be randomized in a 1-to-1 ratio to either mirabegron or tolterodine tartrate for 8 weeks.

E1. Study Overview

E2. Study Medication and Placebo

E2.a Dosing Regimen

Participants will be instructed to take one tablet and 1 capsule (total of 2) of blinded study medication once a day, orally, for 8 weeks. They will start with a Mirabegron (25mg) or tolterodine tartrate (4 mg) dose of study medication and will have the option of dose escalation to 2 tablets and 2 capsules (total of 4) per day (Mirabegron 50mg or tolterodine tartrate 4 mg + identical placebo).

- Mirabegron (25 mg or 2 X 25 mg) with participant-directed dose adjustment
- Detrol LA (4mg or 4mg + placebo) with participant-directed dose adjustment

E2.b Study Medication Supply

Mirabegron (Myrbetriq), tolterodine tartrate (Detrol LA) and placebo tablets identical to the tolterodine tartrate tablets administered in the study will be supplied by Astellas, shipped to the UCSF Pharmacy, and labeled by the pharmacist with randomization numbers. Because the two treatments cannot be made identical, the study will use a double-dummy methodology with the placebo identical to the tolterodine tartrate but these will not be identical to the Mirabegron. Specific procedures for shipping, storing, labeling, logging and returning study medication and for dispensing study medication to participants will be described in detail in the Operations Manual.

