1.1.1 E2.c Study Medication Accountability

Study Medication Accountability Forms and logs will be used to maintain accurate records of receipt, dispensing, return, and disposal of study medication. When drug is received, the

date, randomization number and quantity of drug received will be recorded. During the study, participants receiving study medication should be identified on the drug accountability form by study-specific participant number and acrostic. In addition, the date and quantity dispensed should be recorded each time study medication is dispensed.

All study medication receipts, dispensing, transfers, returns, and disposal of drug are to be documented on the study medication accountability form. Specific procedures for the drug accountability of study medication will be included in the Operations Manual.

E2.d Study Drug Disposal

All doses of study medication that remain undispensed at the end of the study should be properly disposed per UCSF Pharmacy guidelines. It is the responsibility of the Investigator or designee to determine investigational drug accountability, complete the record and ensure that the unused investigational drug is destroyed.

Specific procedures for study medication handling will be included in the Operations Manual.

E3. Titration Sequence

	Baseline (V1)		Phone Call Week 2 (V2)		Week 4 (V3)		Week 8 (V4)
1	Mirabegron 25mg	→	↑ Mirabegron 50mg if desired	→	Same or adjust Mirabegron	→	Final Data
2	Tolterodine tartrate 4mg	→	↑ tolterodine tartrate 4mg + Matching placebo if desired	→	Same or adjust tolterodine tartrate 4mg + Matching placebo	→	Final Data

E4. Evaluation criteria

Primary efficacy will be measured as change in the number of urge incontinent episodes per day from baseline to 8 weeks. A reliable and validated 3-day voiding diary will be used that includes frequency of micturitions (diurnal and nocturnal) and incontinence episodes classified by clinical type (urgency, stress, or other) along with time of occurrence, waking and bedtime.¹⁶⁻

¹⁸ Details recorded in diary:

- Time arose from and time went to bed
- Time of every micturition
- The participant will rate their degree of urgency with each micturition episode
- Time of every incontinence episode
- The participant will report the reason for the incontinence episode (urgency, stress, other)

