The daily voiding diary period is defined as follows: "Awake Time" begins from the time the subject starts her day (time arose) until she goes to bed for that day. "Bed Time" is defined as the time the subject went to bed until she awoke to start the next day.

E5. Evaluation Schedule

Time of Visit	Tele-phone	SV	Base line	2wk phone	4wk	8wk	ET
Telephone Screening	X						
Information & Informed Consent		X					
3-day voiding diary Instruction		X					
Demographics		X					
Alcohol and Tobacco Use		X					
Medical History		X					
Mini-Mental Status Exam (MMSE)*		X					
Geriatric Depression Scale (GDS)*		X					
Concomitant Medication		X					
Dipstick urinalysis		X				X	X
PVR assessment		X				X	X
Voiding diary Review			X		X	X	X
Height^ and Weight			X			X	
Vital Signs		X	X		X	X	X
Health and Medications Update			X	X	X	X	X
Inclusion/Exclusion/Randomization			X				
Dispense study medication			X		X		
California Verbal Learning Test – Short Form (CVLT-SF)			X			X	X
Digit Span			X			X	X
Trail Making Test Parts A & B			X			X	X
Digit Symbol Substitution Task (DSST)			X			X	X
Pittsburgh sleep quality index (PSQI)			X			X	X
Epworth Sleepiness Scale (ESS)			X			X	X
Physical Function and Mobility: Short Physical Performance Battery (SPPB)			X			X	X
IADL			X			X	X
OAB-questionnaire			X			X	X
Patient Perception of Cognitive Change				X	X	X	X
Adverse events (self-report)				X	X	X	X

Patient Perception of Bladder Condition				X	X	X	X
Participant directed Dose Adjustment				X	X		
Assess study medication compliance				X	X	X	X
Trial medication return/count					X	X	X
Early Termination Report							X
Participant Satisfaction						X	X

[^] Height only at baseline visit

* The MMSE and the GDS will be used only as screening tests to determine eligibility, not as outcome measures

E6. Study Visits

The 8-week RCT requires 2 telephone visits (Telephone Screening, Week 2 Phone Call) and 4 in-clinic visits (Screening, Baseline, Week 4, Week 8 (or Early Termination) visit).

E6.1 Recruitment Phase

Women will be recruited by (1) direct, community-based efforts using large media (newspaper notices, television ads, etc.) and small media (brochures in local businesses, talks to local community, notices in churches, salons etc.); (2) seeking referrals from physician's offices (specifically in urology, urogynecology, gynecology, primary care, and geriatric medicine) and (3) purchasing targeted mailing lists.

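### E2.b names no placebo matching mirabegron, so as written the tolterodine arm cannot receive the tablet-plus-capsule set and the stated staff blinding is not delivered

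*Combined protocol and SAP*

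**What the plan says.** **Regimen (E2.a).** Participants in both arms are to "take one tablet and 1 capsule (total of 2) of blinded study medication once a day", with the "option of dose escalation to 2 tablets and 2 capsules (total of 4) per day". For the comparator, the escalated step is "tolterodine tartrate 4 mg + identical placebo".

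**Supply (E2.b).** Besides the two active drugs, "placebo tablets identical to the tolterodine tartrate tablets administered in the study will be supplied by Astellas". Because the two drugs cannot be made to look alike, the section calls for a "double-dummy methodology with the placebo identical to the tolterodine tartrate but these will not be identical to the Mirabegron".

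**Blinding (E6.4.a).** The investigator, trial personnel and participants are to be blinded. The same section lists the manufactured products as the two drugs and a placebo called identical, without saying to which drug.

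**Handling.** E6.4.a has study staff assign the randomization number, after which the matching drug is distributed; it does not say by whom. In E5 the row "Dispense study medication" is marked at Baseline and Week 4, and return and count at Week 4 and at Week 8 or early termination. E2.c adds: "All study medication receipts, dispensing, transfers, returns, and disposal of drug are to be documented on the study medication accountability form". Section M measures adherence by counting tablets and has coordinators pursue nonadherence. E2.b says that procedures for "dispensing study medication to participants will be described in detail in the Operations Manual".

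**The concern.** A double-dummy design with two dissimilar drugs needs two dummies, one for each. E2.b describes one. If the supply list is complete, a mirabegron kit holds two kinds of unit and a tolterodine kit holds one, so the kit reveals the arm to anyone who has seen both sorts.

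Nothing in these documents keeps drug handling apart from outcome collection. Dispensing at Baseline comes before every post-randomization rating. At Week 4, accountability, a further dispensing and the coordinator's two ratings (perceived cognitive change and bladder condition) fall in one visit (E6.5.b). Staff who recognise the arm could influence the cognitive tests and perceived cognitive change (SA2), the physical performance battery and adverse-event reports (SA3), and satisfaction (SA4). The diary (SA5) is less exposed, since the Week 4 diary is completed before that visit's count, and so are the recruitment counts (SA1). Section K says the SA2 estimates will be used to size a larger trial, so a distorted between-arm difference could carry forward.

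**Working it through.** The plan states no figure to reproduce. The check is a tally of the units each arm needs under E2.a against the products listed in E2.b.

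**Inputs**
- Daily set, both arms: 1 tablet + 1 capsule at the start; 2 + 2 after escalation (E2.a).
- Active units: mirabegron 1, then 2 (25 mg, then 2 x 25 mg); tolterodine 1 at both steps, with a placebo added at the second (E2.a).
- Products: mirabegron, tolterodine, tolterodine-matching placebo (E2.b).

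**Kit tally** (M = mirabegron-type unit, T = tolterodine-type unit)

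| Arm and step | Needed per day | Available from the list | Filled |
|---|---|---|---|
| Mirabegron, start | 1 M active + 1 T placebo | both | 2 of 2 |
| Mirabegron, escalated | 2 M active + 2 T placebo | both | 4 of 4 |
| Tolterodine, start | 1 T active + 1 M placebo | T active only | 1 of 2 |
| Tolterodine, escalated | 1 T active + 1 T placebo + 2 M placebo | T units only | 2 of 4 |

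Two of the four kits can be filled. Extra tolterodine placebo could bring the tolterodine kits up to 2 or 4 units, but all of one kind. The result does not depend on which drug is the capsule. That point is itself unclear: E2.a has a tablet and a capsule, while E2.b calls tolterodine and its placebo tablets and section M counts tablets, perhaps as shorthand.

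The E2.a bullets and the E3 table are used only to count active units. They show dose steps rather than kit contents in both arms, so their silence about a mirabegron dummy is not counted as evidence.

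**Opportunity for recognition** (E5)
- Dispensings per woman: Baseline, Week 4 = 2.
- Return/counts per woman: Week 4, Week 8 or early termination = 2.
- Total: (2 + 2) x 50 = 200 if all attend, that is 100 dispensings and 100 counts.
- The first dispensing precedes all three rating points (Weeks 2, 4 and 8). The first count falls at the second of them.

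These counts show opportunity. They do not measure bias.

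**The case against.** The best reply is that this is a drafting omission. E2.a gives both arms a two-form set of blinded medication, and E2.b calls the method double-dummy; both require a mirabegron dummy. On the literal reading, half the women could not follow E2.a from the first day. The quoted sentence may mean only that tolterodine and its placebo differ in appearance from mirabegron, and the placebo mentioned in E6.4.a could cover one for each drug. Dispensing, accountability and handling are also deferred to the Operations Manual, which may keep raters away from study drug. No section says that raters open or compare kits, and several exposed outcomes are the women's own reports.

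Much of this stands. An omission is plausible. The documents do not say who dispenses or counts, and the Manual may. A woman sees only her own kit, so participant unblinding is possible but not shown. The 200 events are scheduled contacts, not exposures of raters.

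It does not remove the contradiction. No section names the second dummy, and the one description of the placebo ties it to tolterodine. The Manual is cited for procedures, not for which products exist. E2.d gives drug accountability to the investigator or a designee, so the investigator's contact with the units is not ruled out.

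**Conclusion.** The concern holds as a statement about the text. From the listed products, the tolterodine arm's set cannot be filled at either dose step (2 of 4 kits overall), and a supply made up to that list would not deliver the blinding of investigator and personnel claimed in E6.4.a. That conclusion assumes that E2.b is the full product list and that some staff see kits from both arms. It does not say what kits were actually made or that blinding was in fact broken. The size and direction of any bias cannot be derived from the documents.

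**What to change.** Reconcile E2.a, E2.b, E3, E6.4.a and the tablet counts in section M through one kit list, by arm and dose step, giving each unit's form and the product it matches. Name the mirabegron-matching placebo in E2.b and E6.4.a.

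If no such placebo will be supplied:
1. Restate E6.4.a so that it does not claim blinding of the investigator and personnel that the kits cannot support, and describe participant blinding as not assured.
2. State in E2.c, E5 and section M that the pharmacy, or staff who collect no outcomes, will dispense, receive and count study drug.

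A treatment-guess question at Week 8 is optional.

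**Cost.** If E2.b merely omits the dummy, this is a text correction. If the dummy must be added, it is one placebo product:
- Taken over 56 days, per tolterodine woman: 56 x 1 = 56 without escalation; 14 x 1 + 42 x 2 = 98 with escalation from the start of Week 3, kept to the end. For 25 women: 1,400 to 2,450.
- Dispensed, assuming 28 days from Baseline to Week 4 and no other supply: the Baseline kit must allow for escalation, 14 x 1 + 14 x 2 = 42; the Week 4 kit is 28 or 56; total 70 to 98. For 25 women: 1,750 to 2,450, before overage.

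The fallback costs a less favourable blinding statement and pharmacy or separate-staff time for up to 100 dispensings and 100 counts.

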1.1.1 E2.c Study Medication Accountability

Study Medication Accountability Forms and logs will be used to maintain accurate records of receipt, dispensing, return, and disposal of study medication. When drug is received, the

date, randomization number and quantity of drug received will be recorded. During the study, participants receiving study medication should be identified on the drug accountability form by study-specific participant number and acrostic. In addition, the date and quantity dispensed should be recorded each time study medication is dispensed.

All study medication receipts, dispensing, transfers, returns, and disposal of drug are to be documented on the study medication accountability form. Specific procedures for the drug accountability of study medication will be included in the Operations Manual.

E2.d Study Drug Disposal

All doses of study medication that remain undispensed at the end of the study should be properly disposed per UCSF Pharmacy guidelines. It is the responsibility of the Investigator or designee to determine investigational drug accountability, complete the record and ensure that the unused investigational drug is destroyed.

Specific procedures for study medication handling will be included in the Operations Manual.

E3. Titration Sequence

	Baseline (V1)		Phone Call Week 2 (V2)		Week 4 (V3)		Week 8 (V4)
1	Mirabegron 25mg	→	↑ Mirabegron 50mg if desired	→	Same or adjust Mirabegron	→	Final Data
2	Tolterodine tartrate 4mg	→	↑ tolterodine tartrate 4mg + Matching placebo if desired	→	Same or adjust tolterodine tartrate 4mg + Matching placebo	→	Final Data

E4. Evaluation criteria

Primary efficacy will be measured as change in the number of urge incontinent episodes per day from baseline to 8 weeks. A reliable and validated 3-day voiding diary will be used that includes frequency of micturitions (diurnal and nocturnal) and incontinence episodes classified by clinical type (urgency, stress, or other) along with time of occurrence, waking and bedtime.¹⁶⁻

¹⁸ Details recorded in diary:

- Time arose from and time went to bed
- Time of every micturition
- The participant will rate their degree of urgency with each micturition episode
- Time of every incontinence episode
- The participant will report the reason for the incontinence episode (urgency, stress, other)

The daily voiding diary period is defined as follows: "Awake Time" begins from the time the subject starts her day (time arose) until she goes to bed for that day. "Bed Time" is defined as the time the subject went to bed until she awoke to start the next day.

E5. Evaluation Schedule

Time of Visit	Tele-phone	SV	Base line	2wk phone	4wk	8wk	ET
Telephone Screening	X						
Information & Informed Consent		X					
3-day voiding diary Instruction		X					
Demographics		X					
Alcohol and Tobacco Use		X					
Medical History		X					
Mini-Mental Status Exam (MMSE)*		X					
Geriatric Depression Scale (GDS)*		X					
Concomitant Medication		X					
Dipstick urinalysis		X				X	X
PVR assessment		X				X	X
Voiding diary Review			X		X	X	X
Height^ and Weight			X			X	
Vital Signs		X	X		X	X	X
Health and Medications Update			X	X	X	X	X
Inclusion/Exclusion/Randomization			X				
Dispense study medication			X		X		
California Verbal Learning Test – Short Form (CVLT-SF)			X			X	X
Digit Span			X			X	X
Trail Making Test Parts A & B			X			X	X
Digit Symbol Substitution Task (DSST)			X			X	X
Pittsburgh sleep quality index (PSQI)			X			X	X
Epworth Sleepiness Scale (ESS)			X			X	X
Physical Function and Mobility: Short Physical Performance Battery (SPPB)			X			X	X
IADL			X			X	X
OAB-questionnaire			X			X	X
Patient Perception of Cognitive Change				X	X	X	X
Adverse events (self-report)				X	X	X	X

Patient Perception of Bladder Condition				X	X	X	X
Participant directed Dose Adjustment				X	X		
Assess study medication compliance				X	X	X	X
Trial medication return/count					X	X	X
Early Termination Report							X
Participant Satisfaction						X	X

[^] Height only at baseline visit

* The MMSE and the GDS will be used only as screening tests to determine eligibility, not as outcome measures

E6. Study Visits

The 8-week RCT requires 2 telephone visits (Telephone Screening, Week 2 Phone Call) and 4 in-clinic visits (Screening, Baseline, Week 4, Week 8 (or Early Termination) visit).

E6.1 Recruitment Phase

Women will be recruited by (1) direct, community-based efforts using large media (newspaper notices, television ads, etc.) and small media (brochures in local businesses, talks to local community, notices in churches, salons etc.); (2) seeking referrals from physician's offices (specifically in urology, urogynecology, gynecology, primary care, and geriatric medicine) and (3) purchasing targeted mailing lists.

